4.5.10 ASSESSMENT OF COMPLIANCE

Participants will be asked to declare the number of days of contact lens wear and the number of times the intranasal device has been used.

4.6 NON-STANDARD OPTOMETRIC PROCEDURES:

4.6.1 INTRANASAL EXAMINATION

The intranasal examination can be completed without topical anesthesia using a nasal speculum. The speculum is gently inserted into the lower end of each of the nares. A light should be utilized to enhance visualization. The speculum is opened to expand the nares such that the nasal cavity can be carefully inspected.

The nasal cavity is inspected for gross ulceration, mass lesions, severe septal deviations or evidence of prior surgery/cautery. Any other gross abnormalities or irregularities should be documented accordingly.

4.6.2 THREE-MINUTE SCHIRMER TEST WITH COTTON SWAB NASAL STIMULATION

At the Screening Visit, the Schirmer test should be performed using cotton swab nasal stimulation. New anesthetic drops should be instilled following the same procedure specified in steps #1 to 3 in Section 4.5.6 above.

1. With new strips in place, the participant should be instructed to hold the cotton swabs and gently probe both nasal turbinates simultaneously, resting intermittently before probing again if necessary. The examiner should continuously coach the participant on how to perform this test properly.
2. The Schirmer strips should remain in place until three minutes have elapsed or both strips have reached maximum score or until both eyes have responded with minimal inclusion criteria of at least an increase of 4 mm compared to Basal Schirmer Scores.

Both Schirmer scores will be recorded and verified that they meet the inclusion criteria.

5 PARTICIPANT TRAINING, DISPENSING AND HOME USE OF TRUETEAR

On Day 0, participants randomized to the TrueTear group will be provided a TrueTear device and disposable tips to take home with them and use daily. Participants will be instructed to use the device as described in the Patient Guide. They will receive training to perform intranasal neurostimulation and will receive a copy of the Patient Guide.

For TrueTear application, participants will be told to turn on the unit by holding down the + button for approximately two seconds. There are five stimulation intensity levels and participants may adjust the level by pressing the + or – buttons to obtain a gentle tingling sensation. They will be instructed to fully insert the tips of the TrueTear into both nostrils simultaneously towards the top and front of the nose (as in Figure 5). Participants will be told they can cease stimulation by holding down the – button for approximately two seconds on the base unit or by withdrawing the tips from the nostrils. Participants will be instructed to replace the Tips with a new one if they do not feel any sensation.

For the initial in-office device application at Day 0, each participant will be trained on the device consistent with instructions in the patient guide. At Day 0 follow up and 1 week, trained clinical personnel will review procedures for the proper use of the device (e.g., correct positioning intranasally, frequency and duration of use, daily replacement and disposal of tips, etc.) with participants.

Figure 5: Use of the TrueTear: (L) Starting position and (R) Correct application position by inserting the disposable tips fully into the nasal cavity and to the front of the nose.

6 PARTICIPANT TRAINING, DISPENSING AND HOME USE OF TRUETEAR SHAM CONTROL

On Day 0, participants randomized to the TrueTear sham control group will be provided a TrueTear sham control device and disposable tips to take home with them and use daily. Participants will be instructed to use the device as described in the Patient Guide. They will receive training to perform intranasal neurostimulation and will receive a copy of the Patient Guide.

For TrueTear sham control application, participants will be instructed to fully insert the tips of the sham device into both nostrils. Participants will be told to apply and control the intensity of stimulation by pressing the plus (+) or minus (-) buttons on the device. When using the device, participants will be told the LEDs on the device are illuminated when stimulation is being delivered, even if they do not feel a “tickle” sensation. Participants will be told they can cease stimulation by pressing the minus button on the device or by withdrawing the device from the nostrils.

For the initial in-office device application at Day 0, each participant will be trained on the device, consistent with instructions in the patient guide. At Day 0 follow up and 1 week, trained clinical personnel will review procedures for the proper use of the device (e.g., correct positioning intranasally, frequency and duration of use, daily replacement and disposal of tips, etc.) with participants.

7 MONITORING PROTOCOL ADHERENCE

Guidelines to be included on adherence to visit windows and windows around other data collection points (i.e. subjective ratings). Procedures for monitoring and reporting deviations from the windows are described in the protocol.

8 POTENTIAL RISKS AND BENEFITS TO HUMAN PARTICIPANTS

This is a non-significant risk (NSR) device study because of the use of marketed products and standard optometric assessments. This device has been granted marketing authorization by the US Food and Drug Administration (FDA) for the purpose of temporarily increasing tear production during stimulation.

Contact lenses in this study will be worn on a daily wear basis, with the participant continuing with their normal lenses and solutions, and with lenses being worn in accordance with their normal wear schedule. Adverse events and/ or complications in daily wear of soft contact lenses can occur (e.g.: inflammation and infection). When contact lenses are worn on a daily wear basis there is a small risk of an adverse event compared to not wearing contact lenses.

Anticipated risks from use of TrueTear may include: an increase in nasal secretions, uncomfortable sensations, epistaxis and other nasal irritations. The full list of potential adverse events from the use of the device is detailed in section 9 (Adverse Events) below.

Anticipated benefits may be a reduction in CL discomfort symptoms and longer comfortable wearing time of CLs over the course of the study.

9 ADVERSE EVENTS

See CCLR SOP012 for a description of adverse event definitions, adverse event management and reporting.

9.1 ADVERSE EVENT RECORDING

All AEs spontaneously reported by the participant and/or in response to an open question from study personnel or revealed by observation, physical examination or other diagnostic procedures will be recorded on the appropriate pages of the CRF. Any clinically relevant deterioration in clinical finding is considered an AE and should be recorded. When possible, signs and symptoms indicating a common underlying pathology should be noted as one comprehensive event.

9.2 ADVERSE EVENT EVALUATION

The Investigator should evaluate if each AE is serious, related to the applicable study device and anticipated using the following definitions.

A serious adverse event (SAE) is defined as any untoward medical occurrence that:

- It results in death (i.e., the AE actually causes or leads to death);
- It is life threatening (i.e., the AE places the participant at immediate risk of death);
- It requires or prolongs inpatient hospitalization. If a participant is hospitalized to undergo a medical or surgical procedure as a result of an AE, the event responsible for the procedure, not the procedure itself, should be recorded as the event. For example, if a participant is hospitalized to undergo coronary bypass surgery, the heart condition that necessitated the bypass should be recorded. Hospitalizations for diagnostic or elective surgical procedures or hospitalizations required to allow outcome measurement for the study should not be recorded as SAEs;
- It results in persistent or significant disability/incapacity (i.e., the AE results in substantial disruption of the participant's ability to conduct normal life functions);
- It results in a congenital anomaly/birth defect in a neonate/infant born to a mother exposed to the investigational device;
- It is considered a significant medical event by the Investigator based on medical judgment (e.g. may jeopardize the participant or may require medical/surgical intervention to prevent one of the outcomes listed above);
- It is considered sight-threatening by the Investigator.

9.2.1 SEVERITY/INTENSITY

All AEs that occur during the course of the study must be reported on the Adverse Event CRF. The Investigator must determine the intensity of the event.

Mild	Awareness of sign or symptom, but easily tolerated
Moderate	Discomfort enough to cause interference with normal daily activities
Severe	Inability to perform normal daily activities

9.2.2 RELATIONSHIP TO THE STUDY DEVICE

Definite	A clear cut causal relationship with the study device and no other possible cause
Probable	A causal relationship with the study device is likely although alternate etiologies are also possible
Possible	A causal relationship with study device is not definite, alternate etiologies are also possible
Not related	The AE has no causal relationship to study device and/or there is evidence of alternative etiology such as concurrent medication or illness.
Not applicable	The participant has not been exposed to the study device.

The AE will be determined to be device related, making it an adverse device effect (ADE), if it is identified to have had a definite, probable or possible causal relationship to the device.

An AE is unanticipated if the nature, severity, or frequency of the event is not consistent with either the known or foreseeable risk of AEs associated with the procedures involved in the research that are described in (a) the protocol-related documents, such as the EC-approved research protocol, user manuals and the current EC-approved informed consent document, and (b) other relevant sources of information such as product labeling and package inserts; or the expected natural progression of any underlying disease, disorder, or condition of the participant(s) experiencing the AE and the participant's predisposing risk factor profile for the AE.

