The critical alpha level for statistical significance will be set at $p \leq 0.05$, with no adjustments for multiple comparisons. All participants who were evaluated will be used in the analysis. In the event of missing data, individual data points will be excluded in the analysis and not extrapolated from the collected data. As this is a proof of concept, additional statistical analysis may be conducted.

Dependent on the outcome of the study, analysis may be conducted on the contact lenses that have been collected. If the decision is made to not analyse the contact lenses then they will be destroyed according to University guidelines.

Additional analyses may be performed to examine the results observed relative to the device usage recorded by the device itself.

Safety assessments include adverse events, visual acuity and slit lamp biomicroscopy. Summaries by application will be prepared of the number and percentage of subjects reporting one or more adverse events, the number and percentage of subjects reporting one or more device-

related adverse events, the number and percentage of eyes with a clinically significant change in visual acuity at each follow-up exam and the number and percentage of eyes with a clinically significant change in slit lamp biomicroscopy at each visit. A clinically significant change in visual acuity is defined as a change of more than 2 lines (logMAR score change greater than 0.2). A clinically significant change in the slit lamp biomicroscopy parameters will be a change of 2 or more grades.

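### In 9.2.2, evidence of another cause is enough by itself for 'Not related', which overlaps 'Probable' and 'Possible', so the device-related adverse event percentage can be understated

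*Combined protocol and SAP*

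**What the plan says.** Section 9.2 of the combined protocol and SAP tells the investigator which definitions to apply: "The Investigator should evaluate if each AE is serious, related to the applicable study device and anticipated using the following definitions".

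Section 9.2.2 then prints a causality scale of five categories. The uncounted category for exposed participants, *Not related*, is worded as follows: "The AE has no causal relationship to study device and/or there is evidence of alternative etiology such as concurrent medication or illness". Two categories above it leave room for another cause. For *Probable* the text reads "A causal relationship with the study device is likely although alternate etiologies are also possible", while *Possible* asks for less and is put in this way: "A causal relationship with study device is not definite, alternate etiologies are also possible". At the top of the scale, *Definite* applies only when every other cause is ruled out. The fifth category is for participants who never received the device.

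Under the rule that closes the scale, an event counts as device-related "if it is identified to have had a definite, probable or possible causal relationship to the device".

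Section 12.1 names two adverse event summaries by application. The first covers participants with any adverse event. The second, limited to events attributed to the device, is introduced with the words "the number and percentage of subjects reporting one or more device".

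Section 9 also points to an operating procedure that is not part of the supplied documents: "See CCLR SOP012 for a description of adverse event definitions, adverse event management and reporting".

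**The concern.** A causality scale works only if each event has one correct category, at least across the line between counted and not counted. Here that line is blurred. *Probable* and *Possible* lie on the counted side and tolerate other causes. *Not related* lies on the uncounted side and can be reached through evidence of another cause, without any judgement that the device played no part.

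At stake is the only summary in 12.1 that attributes adverse events to the device. Two assessors who both follow the text faithfully could code the same event differently, and one of those codings removes it from the device-related count.

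The anticipated events in 9.2.3 suggest that this is a practical problem. Temporary aggravation of nasal allergies presupposes a nasal allergy, so evidence of a concurrent illness comes with the event. Headache, sneezing, rhinorrhea and nasal infection or inflammation can also plausibly have another cause. Section 4.2.4 names colds and active allergies as conditions that may be met at screening.

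**Working it through.** There is no figure in the plan to reproduce. The check compares the definitions and follows the result into the summary.

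**Step 1. The categories side by side (9.2.2).**

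| Category | Role of the device | Other cause | Counted as device-related |
|---|---|---|---|
| *Definite* | clear | ruled out | yes |
| *Probable* | likely | may exist | yes |
| *Possible* | not definite | may exist | yes |
| *Not related*, first limb | none | not required | no |
| *Not related*, second limb alone | no condition stated | evidence required | no |

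*Definite* cannot overlap *Not related* through the second limb. *Probable* also fits within the wording of *Possible*, but both are counted, so that overlap does no harm. The overlap that matters lies between the second limb and *Probable* or *Possible*.

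**Step 2. Two test events.**

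- A participant with a documented cold develops rhinorrhea after using the device, and the assessor thinks the device a likely or possible contributor. The event meets *Probable* or *Possible*, and also the second limb of *Not related*.
- A participant has a headache after use. Another cause is conceivable, but there is no evidence of one. The event meets *Possible* only.

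So the overlap covers counted events with actual evidence of another cause, not all *Probable* and *Possible* events.

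**Step 3. Effect on the summary.** For one arm, let

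- n = participants in the arm;
- R = participants with at least one device-related event when every overlapping event is coded *Probable* or *Possible*;
- k = those among the R whose device-related events all lie in the overlap.

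Section 12.1 counts participants with one or more such events, so a participant drops out only if all of their device-related events are coded *Not related*. The reported percentage therefore lies between (R − k)/n and R/n. The second limb can leave the figure unchanged or lower it, but cannot raise it above R/n.

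**Step 4. Size.** The documents give neither R nor k, and no allocation ratio. If 80 randomized participants (12.1) are assumed to split evenly, one reclassified participant moves an arm's percentage by 1/40 = 2.5 points. With the upper limit of 120 (4.2.2), also split evenly, it is 1/60 = 1.7 points. To show the arithmetic only, with n = 40 and R = 12 assumed:

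- k = 0: 12/40 = 30%
- k = 3: 9/40 = 22.5%
- k = 6: 6/40 = 15%

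These values of R and k have no source in the documents and do not predict this trial's result.

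**The case against.** The strongest case on the other side has five parts.

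- **The overlap is narrow.** Evidence of another cause is more than its possibility. This stands, and it limits the point to events with such evidence.
- **The ordinary reading is sensible.** The label *Not related* suggests that evidence of another cause is meant to support a judgement of no relationship. Many assessors will read it so, but the printed text also permits the other reading and does not say which prevails.
- **The operating procedure may settle it.** It might, and it cannot be checked here. However, 9.2 sends the investigator to the printed definitions, so they should stand on their own.
- **Nothing is lost from the record.** All adverse events go on the CRF (9.2.1), the any-event summary does not use causality, all serious events go to the sponsor whatever their cause (9.3), and the definition of an unanticipated event does not use these categories. This stands in full.
- **Both arms use the same definitions, and those collecting study data are masked (4.1.5).** This makes one-sided coding less likely. It does not remove the ambiguity: each arm's percentage can still be too low. If both arms lost the same fraction f of their counted participants, the difference between them would also shrink, by the factor 1 − f.

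A reader might infer more than the text supports: that device-related harm will be understated, that most of the anticipated events are affected, or that the rate could be halved. The documents do not show how assessors will choose, how often evidence of another cause will be present, or what event rates to expect. The exclusion criteria, which bear on how many participants have nasal allergies, are not in the public text.

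**Conclusion.** The definitional overlap is real and follows directly from the printed wording. An event with evidence of another cause can meet *Not related* and also *Probable* or *Possible*, and the supplied text gives no rule for choosing. The device-related percentage can therefore be understated in either arm. Understatement is possible rather than certain, and its size cannot be computed from the documents.

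The consequence is confined to the adverse device effect classification and the one summary in 12.1 built on it. The comfort and wear-time outcomes are untouched. The conclusion assumes that investigators use the definitions in 9.2.2, as 9.2 instructs, and that no tie-break exists in material not supplied. In an exploratory study with descriptive safety summaries this is a limited defect. It still deserves correction, because a stated rule allows an event likely caused by the device to leave the device-related count.

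**What to change.** In 9.2.2, define *Not related* as an adverse event for which a causal contribution of the device is judged to be excluded, with evidence of an alternative etiology serving as support only. Then add: *Evidence of an alternative etiology alone does not make an AE Not related; if a contribution of the device cannot be excluded, the AE is coded at least Possible.*

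Two details of the wording matter. Merely changing and/or to *and* would remove the overlap, but would leave no category for an unrelated event with no identified cause. The words *at least* are needed so that the added sentence does not move *Probable* events down to *Possible*.

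The cost is a short text change in 9.2.2, carried into any CRF instructions and checked against the operating procedure named in section 9. It is best made before events are coded, to avoid reassessing them. The small downside is that the reported device-related percentage may be somewhat higher.

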9.2.3 ANTICIPATED ADVERSE EVENTS

The following is a list of potential AEs associated with the use of TrueTear or TrueTear sham control:

- Nasal discomfort or pain
- Epistaxis
- Excessive sneezing
- Nasal irritation, paresthesia or numbness post-stimulation
- Nasal infection, abrasion or inflammation

[figure not shown]
- Skin irritation or hypersensitivity
- Headache (e.g., tension, migraine, etc.)
- Facial pain
- Excessive salivation
- Sensation of teeth vibrating
- Excessive rhinorrhea
- Temporary aggravation of nasal allergies
- Allergic reaction to contact materials

9.3 ADVERSE EVENT REPORTING

As per CCLR SOP012, all SAEs (Serious Adverse Events) must be reported by the Investigator to Allergan within 24 hours from the point in time when the Investigator becomes aware of the event.

It is the responsibility of the Investigator to promptly notify the Ethics Committee (EC) of all SAEs and unanticipated problems, per the ECs reporting requirements.

Throughout the course of the proposed study, all efforts will be made to remain alert to possible adverse experiences or untoward findings. If adverse experiences occur, the first concern will be the safety and welfare of the participant. Appropriate medical intervention will be made.

10 DISCONTINUATION FROM THE STUDY

Participants discontinued from the study will be reimbursed [REDACTED] for their active involvement in the study (including the initial screening visit). Participants may be discontinued at the discretion of the investigator, sponsor or participant. The following is a list of possible reasons for discontinuation from the study:

- Screening failure: Participants will be discontinued if they do not meet the inclusion and exclusion criteria outlined in section 4.2.3.

- Unacceptable performance with products to be used in study: Participants may be discontinued if they are unable to achieve acceptable comfort and /or vision with the study products, or if they are unable or unwilling to use the intranasal device as instructed.
- Positive slit lamp finding: Participants may be permanently discontinued from the study depending on the severity of the condition and on the judgement of the investigator.
- Adverse event: If a participant experiences an adverse event during the study, they may be discontinued based on the clinical judgement of the investigator or at the participant's request.
- Symptoms: If the participant has persistent symptoms, they may be discontinued based on the clinical judgement of the investigator.
- Disinterest, relocation or illness: The participant may choose to discontinue due to reasons within or beyond their control.
- Violation of protocol or non-compliance: The participant will be discontinued if they are unable or unwilling to follow the protocol specified visit schedules and/or study procedures.
- Instillation of topical ocular medication: The participant will be discontinued if they elect / are required to use a topical ocular medication during the study.
- A confirmed positive pregnancy test at any time during the study.
- Lost to follow-up: The participant will be discontinued if they cannot be contacted and do not return for a final exit visit, and if the investigator has made a reasonable effort to contact the participant for a final study visit.
- Premature termination of the study by the sponsor, the CCLR or the Office of Research Ethics at the University of Waterloo.

A discontinuation form will be completed, which requires the signatures of both the participant and the investigator except where the participant is lost to follow-up in which case only the signature of the investigator is required.

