4.2.2 NUMBER OF PARTICIPANTS

Up to 120 eligible participants will be dispensed / randomized with study products, with a target of 80 completing the study. Informed consent will be obtained for all participants prior to their enrolment in the study.

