4.3.4 ARTIFICIAL TEARS AND REWETTING DROPS

The use of artificial tears / rewetting drops is not permitted throughout the study. A participant must cease use of artificial tears / rewetting drops at least three days prior to visit 2, and must commit to not using any of these products throughout the duration of the study period.

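### Section 10 shows no way to stop the device and stay in follow-up, so Visit 4 and 5 outcomes may be lost for reasons related to the outcome

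*Combined protocol and SAP*

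**What the plan says.** Section 10 is written wholly in terms of leaving the study. Three of its reasons are left to discretion:

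- Symptoms: "Symptoms: If the participant has persistent symptoms, they may be discontinued based on the clinical judgement of the investigator".
- Comfort: "Participants may be discontinued if they are unable to achieve acceptable comfort and /or vision with the study products".
- Device use, in the same sentence: "or if they are unable or unwilling to use the intranasal device as instructed".

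Two others are mandatory:

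- Non-compliance: "The participant will be discontinued if they are unable or unwilling to follow the protocol specified visit schedules and/or study procedures".
- Medication: "The participant will be discontinued if they elect / are required to use a topical ocular medication during the study".

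An exit visit appears only in passing, under loss to follow-up: "The participant will be discontinued if they cannot be contacted and do not return for a final exit visit". No readable text lists its assessments.

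Related text elsewhere:

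- Section 2 names CLDEQ-8, comfort ratings, comfortable wear time and total wear time as primary.
- Section 4.5.9 schedules CLDEQ-8 at Visits 1, 4 and 5, and diary comfort on eight days from day 3 to day 24.
- Section 12.1 compares change from baseline between arms visit by visit and leaves missing points out.
- Section 11 places the explanation of the partial deception at the last visit, or at exit for those who leave early.
- Section 4.2.2 gives the numbers: "Up to 120 eligible participants will be dispensed / randomized with study products, with a target of 80 completing the study". Section 12.1 says about 80 will be randomised.

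**The concern.** Everyone enrolled must be symptomatic (Section 4.2.3), and Section 10 sets no threshold for persistent symptoms. A participant who does not benefit could therefore be taken out under the symptom clause, and that is a result the trial needs to record. Someone who leaves before Visit 4 has no scheduled post-baseline CLDEQ-8. Diary entries made before exit are kept, but later ones are not collected. The by-visit tests then compare those who stayed, and staying may depend on symptoms.

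Exits could also differ between arms although data collectors are masked. Only the active device delivers current (Section 4.1.3), so intolerance of stimulation itself can arise only there. Anything collected after the Section 11 debriefing is no longer masked.

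The study is exploratory, but Section 12.1 says its results may guide time points and power for later studies. A distorted estimate would carry over into those.

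**Working it through.** The plan gives no power, effect size, SD or expected dropout, so it has no figure of its own to reproduce. The only anchor is Section 4.2.2: 120 − 80 = 40, and 40/120 = 33%. That is the most that could be lost, for any reason, with the target still met. It is not an expected rate.

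**Model (all inputs assumed).** An earlier score E and the outcome Y are bivariate normal with SD 1 and correlation ρ, scaled so that higher is better. Both are shifted by d in the active arm. A share h of those with E below a cut-off c leaves. With a = c − arm mean:

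- exit rate = h·Φ(a)
- mean of Y among those kept = arm mean + ρ·h·φ(a) / (1 − h·Φ(a))

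The cut-off is set so that exits average q over the two arms, with d = 0.50 and ρ = 0.4 or 0.6. Because the key clauses are discretionary, h = 0.5 is the main case and h = 1 the upper case.

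**One case in full** (h = 0.5, q = 10%, c = −0.618):

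- Sham: a = −0.618, Φ = 0.268, φ = 0.330. Exit 13.4%. Shift = ρ × 0.165/0.866 = 0.190ρ.
- Active: a = −1.118, Φ = 0.132, φ = 0.214. Exit 6.6%. Shift = ρ × 0.107/0.934 = 0.114ρ.
- Estimate = 0.50 − 0.076ρ = 0.470 (ρ = 0.4) or 0.454 (ρ = 0.6).

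**Equal rule in both arms, true effect 0.50 SD**

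| Mean exits | Half below cut-off leave (ρ 0.4 / 0.6) | All below cut-off leave (ρ 0.4 / 0.6) |
|---|---|---|
| 5% | 0.476 / 0.463 | 0.464 / 0.446 |
| 10% | 0.470 / 0.454 | 0.445 / 0.417 |
| 20% | 0.477 / 0.465 | 0.418 / 0.377 |

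The main case loses 0.02 to 0.05 SD; the upper case loses 0.04 to 0.12. The standard error with 40 per arm is √(2/40) = 0.22 SD, so the main-case loss is at most about one fifth of it. For a later study with 80% power and two-sided 5%, 0.454 to 0.477 means about 70 to 77 per arm instead of 64. With d = 0 the two shifts cancel and the bias is zero.

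**Unequal exits** (cut-off at the sham 20th percentile, ρ = 0.4 / 0.6)

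- No true effect, 10% active against 5% sham: 0.033 / 0.049 SD in favour of active.
- No true effect, 20% against 10%: 0.078 / 0.117.
- True effect 0.50, exits in active only: 0.534 / 0.551 at 4.5% exits, 0.571 / 0.607 at 9%.
- At ρ = 0.1 the bias in these cases falls to about 0.01 to 0.02 SD, and at ρ = 0 it is nil.

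**Direction.** If a fixed share m of an arm leaves from the low end of a score correlated ρ with the outcome, the mean of those kept shifts by ρ·φ(z)/(1 − m), where z is the m quantile. Losing 5% of active and 25% of sham gives (0.109 − 0.424)ρ = −0.315ρ, which is −0.09 to −0.16 SD at ρ = 0.3 to 0.5. Losing 30% of active and 10% of sham gives (0.497 − 0.195)ρ = 0.302ρ, which is +0.09 to +0.15. The sign follows the arm that loses more.

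**Effect of including off-device follow-up.** If benefit ends when the device is stopped, the estimate is 0.50 × (1 − active exit rate). With active exits of 2.9%, 6.6% and 15.2% in the three main cases, that is 0.485, 0.467 and 0.424.

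**The case against.** The strongest objection is that this is an argument from absence in a redacted document. Section 4.4.2 is not visible, and parts of Sections 4.1.1, 4.5 and 12.1 are blacked out. Exit assessments would normally be described in such places. This stands: a reader might infer that no outcomes are taken at exit, and the documents do not show that.

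Nor is overlap with the outcomes certain. The symptom, comfort and device-use clauses are permissive, and symptoms are undefined. The comfort clause concerns study products, a term Section 4.2.2 uses for what is randomised, so it may partly mean tolerability of the device. A reader might also infer that using rewetting drops forces an exit. Section 4.3.4 says only that participants "must commit to not using any of these products throughout the duration of the study period". It states no consequence, although the non-compliance rule could be applied.

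On size, the equal-rule loss is small against the standard error. The unequal-exit figures assume that leaving tracks the outcome, whereas stimulation intolerance may have little to do with lens comfort. Section 9.2.3 lists mainly nasal, facial and headache events, and lists them for both devices, so active-only exits are an extreme case. This also stands, and at ρ = 0.1 little bias remains.

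Finally, counting off-device time changes the question to the effect of being assigned the device. At 20% exits it gives 0.424, further from 0.50 than the 0.465 to 0.477 among those who stayed. That rules out claiming that follow-up brings the estimate closer to the on-device effect. It does not remove the reason to collect the data. Section 10 as written can end collection for outcome-related reasons, and no later analysis can restore what was not collected.

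**Conclusion.** The point holds as a modest, inexpensive improvement. As far as the text can be read, Section 10 has no status between on device and out of the study. Some of its exit reasons can overlap the primary outcomes, and Section 12.1 then analyses whoever remains. The Visit 4 and 5 comparisons may therefore be among selected participants.

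The size is unknown because every input beyond 120 and 80 is assumed. Under one equal rule the effect is probably small: 0.02 to 0.05 SD off a true 0.50, and nothing if there is no effect. Bias in either direction needs two conditions together: exits that differ by arm and exits related to outcome. The documents make the first plausible but establish neither. A reader might take the 33% as a forecast of dropout, or conclude that non-responders will be removed; neither follows from the text.

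**What to change.** In Section 10:

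- Record stopping the device separately from withdrawing from the study.
- For those who stop the device without withdrawing consent, continue the existing phone CLDEQ-8 and online diary on the original schedule to Visit 5. Record device, lens-wear and drop status each time. Study exit and the Section 11 debriefing then fall at the end of that follow-up.
- For anyone leaving the study, take CLDEQ-8, comfort, comfortable wear time and total wear time at the exit visit, before the debriefing. If text not visible here already requires this, confirming it is enough.

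In Section 12.1 and the report:

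- Tabulate exits by arm and reason.
- Show the by-visit comparisons with and without off-device records. Which is the main one is the sponsor's choice of question.
- Report by arm how many stopped lens wear, and set their wear time to zero in a sensitivity analysis only.

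No clinical stopping decision changes, and nobody is asked to keep using the device or lenses. The cost is protocol wording that needs ethics review (Section 15.2), a later debriefing for those who stop the device, and a second estimate that includes off-device time and may be diluted.
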